**1a) Is this study considered human research?**

- Yes
- No
- I don't know

**1b) Please select:**

- This is an application for a NEW human subject research protocol
- This is a revision of an existing protocol

Was this study initially approved prior to January 21, 2019?

- Yes
- No

Were you instructed to convert to the 2018 Common Rule Requirements?

Yes  No

## Section 2 - Research Subjects

### 2a) What is the total planned number of VA-consented subjects?

Include the total number of subjects who will prospectively agree to participate in the study (e.g., documented consent, oral consent, or other).

32

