### 2b) What is the total number of VA subjects who WILL NOT be consented?

Include the total number of subjects that will be included without consent (e.g., chart review). *Note: Data about people are still considered "human subjects" by the IRB, so even if you do not intend to contact the patients whose charts you will review, you still should enter the number of charts as your "planned subjects."*

0

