## Section 6 - Specific Aims

### 6) Provide a statement of specific aims and hypotheses that serve as the basis for this protocol. Emphasize those aspects that justify the use of human subjects.

In preparation for a full-scale study via a subsequent Merit Review IIR proposal, our overall study objective is to adapt and combine two existing interventions for a new population, and to examine the feasibility and acceptability of conducting a randomized controlled trial of an enhanced yoga + MR mind-body intervention for reducing pain-related disability and pain while improving function in Veterans with PTSD. The study will be conducted in two phases: the first phase will involve adapting and combining two existing mind-body interventions for Veterans with PTSD and chronic pain and creating instructor and home practice manuals for the intervention. The second phase will recruit and randomize 32 military personnel with chronic pain and PTSD to either enhanced yoga (yoga plus MR training) or a relaxation/health education (R/HE) comparison group.

The specific aims are as follows:

Aim 1: Expert collaborators will refine and combine the existing Yoga for cLBP and/or chronic neck pain (cNP) intervention with a shorter version of [name], Repetition Program (MRP).

Aim 2: Create revised instructor and home practice manuals.

Aim 3: Examine the feasibility of recruitment, retention, assessments, randomization, adverse events, and acceptability of an enhanced yoga intervention for reducing disability and chronic pain among Veterans with PTSD via a pilot randomized controlled trial.

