C1.1. Aim 1 & 2: The interventions will be adapted in four main ways; a) to safely benefit cNP patients; [b) to ensure it is trauma-sensitive; c) includes additional emphasis on relaxation and stress reduction; and d) to include shorter MRP training sessions. Aims 1 and 2 will leverage ongoing work from the PI's current NCCIH-funded R34 in which the yoga for clBP intervention is being adapted to benefit cNP patients. To ensure trauma-sensitivity, study investigators will build on an intervention designed by co-inv. [name] and other study RR&D-funded protocols (Drs. [name] and [name]) to align the intervention with principles outlined by Emerson et al. The additional relaxation and stress reduction emphasis is designed to alleviate PTSD symptoms in addition to chronic pain.] The MRP will be shortened to an initial 30-minute training followed by 15-minute brief interventions sessions and home practice assignments by [name] who has done preliminary work on adapting MRP for briefer sessions and delivery by phone or Internet. Study investigators will review literature, other protocols, and the revised MRP prior to participating in a half-day intervention refinement conference at VASD. Further intervention refinement will occur at project meetings and a manual will be produced.

C1.2. Aim 3: [we will recruit and randomize 32 VA patients formally diagnosed with PTSD and chronic clBP and/or cNP to enhanced yoga or the R/HE control. We plan to recruit starting in month 4, and will begin randomizing when we reach enrollment of 16, which is expected by month 6-7. The first set of interventions will start in month 8 and run for 12 weeks. We will repeat this process with ongoing recruitment of another 16 participants between months 8-12, with interventions running months 13-16. Participants will complete physiological and self-reported outcomes assessments at baseline, 12 weeks, and 18 weeks after enrollment. Assessments will take about 40 minutes each and participants will be compensated \$40 for each completed assessment. We will also conduct qualitative interviews with 7-8 yoga participants and 4-5 R/HE comparison participants to obtain in-depth feedback on satisfaction and areas that could be improved before a larger trial is conducted.] If feasibility, acceptability, and safety are established, the primary health outcome of interest for a subsequent trial is pain-related disability/ functioning (Roland Morris Disability Questionnaire (RMDQ)).

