C2. Recruitment. We will recruit a total of [32 Veterans] over the course of 8 months. Co-I [name] serves as Director of Outpatient Mental Health at the Medical Center and meets regularly with providers and the directors of the other mental health clinics, and will orient them to study goals. [name] is Director of the Behavioral Medicine Service and part of the Mental Health Integration Team. She serves as a liaison between mental health clinics and primary care, and also treats and evaluates chronic pain patients. [name] will alert primary care and mental health providers to study goals and criteria. [name] also has experience recruiting chronic pain patients with the help of [name] in primary care clinics and through [name] of the Pain Management service. VA patients will be directly targeted via flyers posted in common areas of VA facilities. In sum, study investigators have extensive experience recruiting PTSD and chronic pain patients at VASD, where ~ 40,000 Veterans have chronic pain, 10-15,000 have PTSD, and 5-6,000 have both conditions. *In-person recruitment will be limited and conducted following RAMP up guidelines, including social distancing, the use of PPE, COVID-19 consent addendum, and COVID-19 symptom screening.*

C3. Screening and Inclusion/Exclusion Criteria. Recruitment staff will conduct a brief pre-screen by phone and schedule interested patients for a screening visit to obtain informed consent and HIPAA authorization. Inclusion/exclusion criteria will be applied using a chart review of the VA medical record, a standard medical history interview, and the screening measures described below. English literacy is required. Participants are asked to not perform other mind-body therapies during the study. *Due to COVID-19 pandemic, procedures have been developed to conduct the formal study clinical screening remotely whenever possible to limit in-person research activities. In-person screening for subjects at normal risk will be conducted following RAMP up guidelines, including social distancing, the use of PPE, COVID-19 consent addendum, and COVID-19 symptom screening.*

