## Section 9.9 Data Safety Monitoring Board or Plan

## 9.9) Provide a Data Safety Monitoring Plan (DSMP) or the details of a Data Safety Monitoring Board; if a written plan is available, attach a copy of the plan to the submission form.

The study is a pilot intervention that will randomize 32 participants with PTSD to either yoga plus Mantram repetition or to a relaxation comparison group. Study investigators will review all adverse events on a weekly basis and report them as appropriate to the IRB according to established requirements. Drs.[name] and [name] have clinical and research expertise with PTSD. If the rate of serious adverse events attributed to either intervention results in an imbalanced SEA rate between the two study arms, or is higher than clinically expected, the study will be stopped to assess safety. If adjustments to the intervention to remedy the problem are not obvious or easily made, the study intervention(s) will be discontinued.

Research activities will cease if any participant or study staff member that had recent study interactions with study staff or other participants tests positive for COVID-19 within 3 weeks of those interactions. All at risk persons will be notified of their risk at that time.

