## Section 11 - Recruitment

### 11) Describe, step-by-step, the plans for recruitment of subjects (or selection of subjects as in record review).

**This description must include how, when, and where potential subjects are approached as well as procedures for identifying potential participants (through medical records, physician referral, third-party sources, etc.). Include how selection is equitable. Indicate if vulnerability to coercion may be present and if so plans to ensure voluntary participation.**

Recruitment will occur through flyers posted through VA medical centers, and through clinical providers. Clinical providers will be briefed on the study goals and procedures, risks, and potential benefits. During the enrollment period, clinical providers will personally invite and refer patients to participate, and when appropriate, direct patients to speak with study research staff, who will be available during clinics. Patients who speak with research staff will be given a clear description of all aspects of study participation, including randomization, collection of electronic data, and incentives. Those who wish to enroll and meet entry criteria above by self-report will undergo signed informed consent, after which electronic medical records will be reviewed to confirm, document, and record eligibility criteria.

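### Does item 2a's figure of 32 consented subjects need raising, given that consent comes before eligibility screening?

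*Combined protocol and SAP*

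**What the plan says.** Item 2a asks "What is the total planned number of VA-consented subjects", with an instruction to count everyone who agrees to take part, whatever the form of consent. The entry is 32. Item 2b asks "What is the total number of VA subjects who WILL NOT be consented" and is answered 0.

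The figure of 32 recurs as the randomized number:

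- Section 6: "The second phase will recruit and randomize 32 military personnel with chronic pain and PTSD".
- Section 9, C1.2: the plan is to "recruit and randomize 32 VA patients formally diagnosed with PTSD".
- Section 9.9: "The study is a pilot intervention that will randomize 32 participants with PTSD".

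On the order of events, Section 9, C3 has staff pre-screen by phone and then "schedule interested patients for a screening visit to obtain informed consent and HIPAA authorization". It goes on: "Inclusion/exclusion criteria will be applied using a chart review of the VA medical record", together with a medical history interview and the screening measures. Section 11 says that people who wish to enroll and meet the criteria by self-report "will undergo signed informed consent, after which electronic medical records will be reviewed to confirm, document, and record eligibility criteria".

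The Section 10 prompt asks how many consented subjects are likely to fail screening. The answer, under Screening Measures, cites a failure rate of about 25% at most from a previous study, and from it expects roughly 44 screened and no more than 12 failures.

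**The concern.** Item 2a counts consents, not randomizations. If consent is signed at the screening visit and eligibility is confirmed afterwards, people who fail at that stage are already consented subjects. Section 27 points the same way, because it limits research review of medical records to people who have consented. Section 10 expects up to 12 such failures. On that reading, one application carries two different totals: 32 in item 2a, and about 44 implied by Section 10.

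Two things could be at stake. The headline count might understate how many people are asked to consent and undergo screening. And if 32 were treated as a limit on consents, the trial could fall short of 32 randomized.

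**Working it through.** **Inputs.** Consented, item 2a: 32. Randomized, Sections 6, 9 (C1.2) and 9.9: 32. Screen failure, Section 10: at most about 25%. Screened and failing, Section 10: about 44 and at most 12. Recruitment period, C2: 8 months. Monthly flow, C11.2: 5 screened and eligible for 4 enrolled.

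**1. Reproduce the plan's screening figure.** The number to screen for N randomized at failure rate d is N / (1 - d).

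- 32 / (1 - 0.25) = 42.7, so 43. The plan says about 44.
- 44 - 12 = 32.
- 12 / 44 = 27.3%, against a stated 25%; 25% of 44 is 11.

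The Section 10 figures agree with each other and with 32 randomized to within rounding. Nothing in them is miscalculated.

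**2. Size of the mismatch in item 2a.** 44 - 32 = 12, which is 12 / 32 = 37.5% of the entry. This is an upper figure on Section 10's numbers, because the stated failure rate is itself a maximum:

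| Failure rate after consent | 32 / (1 - d) | Consents needed |
|---|---|---|
| 5% | 33.7 | 34 |
| 10% | 35.6 | 36 |
| 15% | 37.6 | 38 |
| 20% | 40.0 | 40 |
| 25% | 42.7 | 43 |

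Any failure rate above zero takes the consent total past 32.

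**3. Is 44 a safe replacement?** C11.2 expects a further loss between eligibility and enrollment. Over 8 months, 8 x 4 = 32 enrolled needs 8 x 5 = 40 screened and eligible. If that loss falls after consent, the total is 40 / 0.75 = 53.3, so 54. The documents do not say when it occurs. The consent total therefore lies between just above 32 and about 54, and 44 is one point in that range.

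**4. Would the trial come up short?** If recruitment stopped at 32 consents and 25% failed, 32 x 0.75 = 24 would remain, or 12 per arm instead of 16. That requires item 2a to act as a cap. No section says so. C1.2 starts randomizing once 16 are enrolled and then repeats with another 16 (16 + 16 = 32), and Section 10 plans for about 44 screened. The shortfall contradicts the plan's own procedure.

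**5. Does any analysis use item 2a?** The C11.2 criteria are enrolled participants per month, attendance, retention, satisfaction, serious adverse events by arm, questionnaire time and instructor fidelity. C11 adds a recruitment-to-enrollment ratio, which will be computed from observed counts. None takes the planned consent total as an input.

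**The case for a change.** The best case for a change is textual. Item 2a's instruction turns on consent. C3 and Section 11 both put signed consent ahead of the chart review. The Section 10 prompt asks specifically about consented people who fail, and its answer follows directly on the list of screening measures, so it is hard to read the 44 as a count of phone calls before consent. Anyone consented beyond 32 appears in neither item 2a nor item 2b. Disclosure in Section 10 does not by itself reconcile the two entries, and correcting one figure would cost almost nothing.

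Most of that stands as a description. The two entries do not match, and only zero failures after consent would make 32 literally right.

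Two parts are weaker. The documents never state that 44 people will consent. The phone pre-screen and the self-report check come before consent and will remove some people, and the answers to items 12a, 12.1a and 12.9c, which bear on screening before consent, cannot be read in the available text. Nor is the proposed correction secure: putting 44 in item 2a could leave it at odds with the 5-to-4 flow in C11.2. The applicant evidently entered study participants where the form asked for consents, which is a mismatch of definition and not a faulty calculation.

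**Conclusion.** The inconsistency is genuine and clerical. Item 2a carries the randomized number where the form asks for the consented number. On Section 10's figures the gap is up to about 12; it could be larger, with about 54 consents in all, if the eligible-to-enrolled loss follows consent.

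No change follows, for three reasons. The application already states the expected screening load and failures in the section that asks for them, so a reader of the whole form is not misled about the burden. Nothing in the documents makes item 2a a limit, so the fall to 24 randomized does not arise. And the randomized target, feasibility thresholds, safety rules and outcome summaries are the same whichever figure stands in item 2a.

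This rests on taking 32 as the randomized number, as Sections 6, 9 (C1.2) and 9.9 state, and on recruitment continuing until both cohorts are filled. The references to 20 per arm in C11.2 and to blocks of 20 in C4 are a separate matter and do not depend on item 2a. Any institutional rule that treats the item 2a entry as binding lies outside the documents and is not assumed here.

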### 2b) What is the total number of VA subjects who WILL NOT be consented?

Include the total number of subjects that will be included without consent (e.g., chart review). *Note: Data about people are still considered "human subjects" by the IRB, so even if you do not intend to contact the patients whose charts you will review, you still should enter the number of charts as your "planned subjects."*

0

## Section 2.1 Consented Subject Groups

### 2.1) For each of the subject categories listed below, indicate whether or not these subject groups will participate in the study:

#### 2.1a) Children under the age of 18

*Note: If neonates or children will be involved in this study, certification by the Medical Center Director will be required. Only minimal risk research may be performed with children. Only non-invasive monitoring and/or prospective observational and retrospective record review studies that are minimal risk can be conducted in VA involving neonates.*

Yes  No

#### 2.1b) Pregnant women

Yes  No

#### 2.1c) Individuals with cognitive/decisional impairment

Yes  No

#### 2.1d) Non-English-speaking individuals

Yes  No

#### 2.1e) Prisoners of War (explicitly targeting this group)

Yes  No

#### 2.1f) Non-Veterans (Note: Justification for inclusion of non-Veterans will be required)

Yes  No

#### 2.1g) Incarcerated individuals (Note: VA CRADO approval will be required)

Yes  No

#### 2.1h) VA employees - including VA paid, IPA, or WOC (Note: Union review and authorization may be required)

Yes  No

#### 2.1i) Students of the institution (e.g., resident trainees) or of the investigator

Yes  No

2.1j) Patients with cancer (or high cancer risk) [explicitly targeting this group]

Yes  No

### Section 3 - Study Features (these items default to "No" for convenience)

3) This section consists of several Yes/No questions addressing protocol characteristics. [Click on Save and Continue.](#)

#### Section 3.1 Protocol Basics

##### Select all that apply

3.1a) The research **intends to change** the participant.

Yes  No

3.1b) **Interactions** with living participants to collect data or specimens with no intent to change them.

Yes  No

3.1c) This is a study that **never** has any **subject contact and does not collect subject identifiers**

Yes  No

3.1d) This is a **chart review** study involving retrospective or prospective medical records.

Yes  No

3.1e) This is a **multi-site** study occurring in-part or in-full at other locations.

Yes  No

3.1f) There is an **international** component to this research. *International research includes sending or receiving human derived data or specimens (identifiable, limited data set, coded, or deidentified) to or from an international source. International research does not include studies in which VA is only one of multiple participating sites where the overall study-wide PI is not a VA investigator.*

Yes  No

3.1g) This study includes **off-station activity** (not including VA-leased space or CBOC clinics) conducted under VASDHS IRB approval. *Note: this does not include research conducted by a collaborator at their home institution under their institutional approval.*

Yes  No

3.1h) VA subjects will **participate** in part or in full **at other locations** (not including VA-leased space or clinics) under VASDHS IRB approval. *Note: if this study involves remote participation of subjects, please indicate "no" and describe their remote participation in section 9 of the application. This question is intended to understand whether participants must physically go to a non-VA location to participate in this VA research study.*

Yes  No

#### Section 3.2 Specimen Use and Data Repository

##### Indicate whether or not each of the following applies to this protocol

3.2a) Involves specimens that are left over from pathological or diagnostic testing (**non-research specimens**)

Yes  No

3.2b) Involves **specimens collected for research purposes only**

Yes  No

3.2c) This study includes **specimen banking** (specimens are retained for use outside of the purposes of this protocol)

Yes  No

3.2d) The study involves **DNA** genotyping or other **genetic analysis**

Yes  No

3.2e) Biological **specimens/material** will be sent outside of the VA.

Yes  No

3.2f) A **data repository** is maintained (data are retained after completion of the protocol for other uses, IMPORTANT: see ? before checking "yes")

Yes  No

3.2g) **Data will be shared outside** of the VA (identifiable, coded, limited data set, or deidentified)

Yes  No

### Section 3.3 Treatment and Clinical Trials

#### Indicate whether or not each of the following applies to this protocol

3.3a) Includes a **treatment** component (a research treatment)

Yes  No

3.3b) Study is a **clinical trial**. *Note: A clinical trial is a research study in which one or more human subjects are prospectively assigned to one or more interventions (which may include placebo or other control) to evaluate the effects of the interventions on biomedical or behavioral health-related outcomes.*

Yes  No

3.3c) Has a data safety monitoring board (**DSMB**) or data safety monitoring committee.

Yes  No

3.3d) Has a **data safety monitoring plan** (but not a DSMB) (this is not the data security plan, it is a safety plan).

Yes  No

### Section 3.4 Drugs and Devices

#### Indicate whether or not each of the following applies to this protocol

3.4a) **Drugs** that require **FDA** action such as an Investigational New Drug (IND) approval or exemption or 510 (k) approval.

Yes  No

3.4b) Other drugs, supplement, etc. that **do not require FDA** action for inclusion in the study.

Yes  No

3.4c) Medical **devices requiring FDA IDE** approval or waiver

Yes  No

3.4d) **Other medical devices**

Yes  No

## Section 3.5 Risk and Hazards

### Indicate whether or not each of the following applies to this protocol

3.5a) Study places subjects at **greater than minimal risk** (do not include risks that are due to standard care)

Yes  No

3.5b) Human subjects are exposed to **radioisotopes** (do not include standard care).

Yes  No

3.5c) Subjects have other **radiation exposure** (e.g., x-rays) (do not include standard clinical use).

Yes  No

3.5d) Target population has psychiatric diagnosis or behavioral complaint.

Yes  No

## Section 3.6 Clinical Facilities and Standard Care

### Indicate whether or not each of the following applies to this protocol

3.6a) Study **uses VA clinical services** (e.g., adds required tests run in the VA lab for study purposes; research procedures concurrent with clinical care)

Yes  No

3.6b) Includes procedures or drugs that will be considered **part of standard care**.

Yes  No

3.6c) Involves **lab tests done for research purposes**.

Yes  No

